4.7.2. Benefit Assessment

- No clinical benefit is expected for the mild to moderate asthmatics who are to be enrolled into this FTIH study, as evidence for clinical benefits using mepolizumab and reslizumab have been demonstrated in the severe asthmatic population.
- This single ascending dose, FTIH study in mild to moderate asthmatics (with blood eosinophils ≥ 200 cells/ μ L) will not only provide initial safety, tolerability, immunogenicity, and pharmacokinetic data, but also an understanding of the relationship between GSK3511294 dose and blood eosinophil reduction, to better inform dose selection and dosing interval in the subsequent studies of the clinical development program.

4.7.3. Overall Benefit:Risk Conclusion

Although no clinical benefit is expected for recruited participants, overall the benefit:risk balance for this FTIH study to be performed in mild to moderate asthmatics is considered acceptable. The study provides the opportunity to generate key PK and PD data, as well as safety and tolerability information, in an eosinophilic population, thereby supporting subsequent progression into the targeted severe eosinophilic asthma population. Close monitoring of participants for standard safety concerns in FTIH studies of biologics will be performed.

5. SELECTION OF STUDY POPULATION AND WITHDRAWAL CRITERIA

Specific information regarding warnings, precautions, contraindications, adverse events, and other pertinent information on the GSK investigational product or other study treatment that may impact participant eligibility is provided in the IB (Section 3).

Deviations from inclusion and exclusion criteria are not allowed because they can potentially jeopardise the scientific integrity of the study, regulatory acceptability or participant safety. Therefore, adherence to the criteria as specified in the protocol is essential.

5.1. Inclusion Criteria

A participant will be eligible for inclusion in this study only if all of the following criteria apply:

AGE

1. Between 18 and 65 years of age inclusive, at the time of signing the informed consent.

TYPE OF PARTICIPANT AND DIAGNOSIS INCLUDING DISEASE SEVERITY
 
2. Blood eosinophils of ≥ 200 cells/μL at screening.
 
3. Asthma: A physician diagnosis of asthma (mild or moderate, as defined by the Global Initiative for Asthma (GINA), 2017) at least 12 months prior to the start of the study. The reason for diagnosis of asthma should be documented in the participant's source data, including relevant history. If available, investigations – specifically evidence of airway hyperresponsiveness, airflow variation (peak flow rate or FEV₁) or reversible airflow obstruction, should also be documented in the participant's source data.
 
NOTE:
 
 • Airway hyper-responsiveness is defined by a methacholine or histamine concentration of <8 mg/mL producing a $\geq 20\%$ fall in FEV₁. • Airflow variation is defined as a variation in peak flow rate (the difference between the highest and lowest peak expiratory flow rate expressed as a percentage of the average peak expiratory flow rate) of $> 20\%$ over a series of measurements or a variation in FEV₁ $> 15\%$ when measured on separate occasions. • Reversible airway obstruction is defined as increase in FEV₁ of $\geq 12\%$ over baseline AND an absolute change of ≥ 200 mL, following 4 inhalations of albuterol/salbutamol inhalation aerosol/spacer (or equivalent nebulised treatment with albuterol/salbutamol solution). 
4. Asthma status: A screening pre-bronchodilator FEV₁ $\geq 60\%$ of predicted normal value.
 
 • NOTE: Predicted values based upon European Respiratory Society guidelines [Quanjer, 2012]. 
5. Asthma control: Asthma Control Test score > 19.
 
6. hsCRP of < 10 mg/L at screening.
 
7. Otherwise healthy (other than the acceptable conditions of asthma and other atopic diseases, including allergic rhinitis and atopic dermatitis) based on a screening medical history, physical examination, vital signs, ECG assessment, pulmonary function testing, and clinical laboratory results.
 
NOTE: A participant with abnormal clinical laboratory parameter(s), which is/are not specifically listed in the inclusion or exclusion criteria, outside the reference range for the population being studied may be included only if the investigator (in consultation with the Medical Monitor) agree and document that the finding is


unlikely to introduce additional risk factors and will not interfere with the study procedures. In the event of out-of-range results of safety tests, the tests may be repeated once within the screening window. If a retest result is again outside the reference range and considered clinically significant by the investigator and GSK medical monitor, the participant will be considered a screen failure.

8. Asthma therapy:

- Maintained controlled on as needed SABA and one of the following:
- stable dose of ICS
- stable dose of combination therapy: ICS/LABA

NOTE: the ICS dose should be up to a maximum daily dose shown in Table 2, and stable for at least 12 weeks prior to the study treatment.

Table 2 Maximum Allowed Daily Doses of Inhaled Corticosteroid (ICS)

Inhaled Corticosteroid	Max Daily Dose (µg)
Beclomethasone dipropionate (CFC)	1000
Beclomethasone dipropionate (HFA)	400
Budesonide (DPI)	800
Ciclesonide (HFA)	320
Fluticasone propionate (DPI)	500
Fluticasone furoate (DPI)	100
Mometasone furoate	440
Triamcinolone acetonide	2000

CFC –Chlorofluorocarbonate, DPI – Dry Powder inhaler, HFA-: hydrofluoroalkane propellant

WEIGHT

9. Body weight ≥ 50 kg, and **body mass index (BMI)** of 19-32 kg/m² inclusive.

SEX

10. Male and female participants.

- a. Females: a female participant is eligible to participate if she is not pregnant (see [Appendix 6](#)), not breastfeeding, and not a woman of childbearing potential as defined in [Appendix 6](#).
- b. Males: as GSK3511294 is a monoclonal antibody that is not anticipated to interact directly with Deoxyribonucleic acid (DNA) or other chromosomal material with minimal exposure through semen expected, male participants will not be required to use contraception during the study, nor are they prohibited from donating sperm.

INFORMED CONSENT

11. Capable of giving signed **informed consent** as described in Section 10.2, which includes compliance with the requirements and restrictions listed in the consent form and in this protocol.

5.2. Exclusion Criteria

A participant will not be eligible for inclusion in this study if any of the following criteria apply:

CONCURRENT CONDITIONS/MEDICAL HISTORY (INCLUDES LIVER FUNCTION AND QTc INTERVAL)

1. **Asthma exacerbation:** Any asthma exacerbation requiring systemic corticosteroids within 12 weeks of screening, or that resulted in overnight hospitalization requiring additional treatment for asthma within 6 months prior to screening.
2. **A history of life-threatening asthma.** Defined as an asthma episode that required intubation and/or was associated with hypercapnia, respiratory arrest or hypoxic seizures within the last 5 years.
3. **Significant pulmonary diseases, other than asthma, including (but not limited to):** pneumonia previously requiring hospital admission, pulmonary fibrosis, bronchopulmonary dysplasia, chronic bronchitis, emphysema, chronic obstructive pulmonary disease, or other significant respiratory abnormalities.
4. **Respiratory Infection:** Suspected or confirmed bacterial or viral infection (including tuberculosis) of the upper or lower respiratory tract, sinus or middle ear that occurred within and/or has not resolved within 4 weeks of screening that:
 - led to a change in asthma management
OR
 - in the opinion of the Investigator, is expected to affect the participant's asthma status or the participant's ability to participate in the study.

NOTE: Participants can be rescreened once to allow for an adequate time period between resolution of the infection and randomisation.

5. Positive for **hepatitis B** surface antigen (HBsAg) at screening. (Please refer to [Appendix 8](#) for country specific requirements for Germany)
6. Positive **hepatitis C** antibody test result at screening, or within 3 months prior to first dose of study treatment.

NOTE: Participants with positive Hepatitis C antibody due to prior resolved disease can be enrolled, only if a confirmatory negative Hepatitis C Ribonucleic acid (RNA) Polymerase chain reaction (PCR) test is obtained. Test is optional and participants with negative Hepatitis C antibody test are not required to also undergo Hepatitis C RNA testing.

7. Known **immunodeficiency** (other than that explained by the use of corticosteroids), including a positive test for **HIV** antibody at screening.

8. **Latent or chronic infections** (e.g., genital herpes, urinary tract infections) or at risk of infection (e.g., significant trauma or infection within the 90 days before screening).
9. **Opportunistic infection** within 6 months prior to screening (e.g., a non-tuberculous mycobacterial infection or cytomegalovirus, pneumocystosis, aspergillosis).
10. **Parasitic infestation** within 6 months prior to screening, or have travelled to a country with a high prevalence of such infections in the 6 months before screening, or intend to do so in the year after dosing.
11. **Live vaccine** within 4 weeks prior to screening, or intention to receive live vaccine during the study.
NOTE: Attenuated or non-live vaccines are acceptable, if > 5 days before dosing.
12. **QTcF > 450 msec.**
NOTES:
 - The QTc is the QT interval corrected for heart rate, for the purposes of standardisation, QTc corrected by Fridericia's formula (QTcF) will be used across sites with central over-read to limit variability.
 - For purposes of data analysis, QTcF or a composite of available values of QTc will be used as specified in the Reporting and Analysis Plan (RAP).
13. A personal history of **severe hypertension, arrhythmia, Right Bundle Branch Block, or Left Bundle Branch Block**, or a family history of **sudden unexplained death, long QT, familial cardiac syndrome, or cardiomyopathy**.
14. **Alanine aminotransferase (ALT) >1.5xUpper limit of normal (ULN).**
15. **Bilirubin >1.5xULN.** Isolated bilirubin >1.5xULN is acceptable if bilirubin is fractionated and direct bilirubin <35%.
16. **Current or chronic history of liver disease**, or known hepatic or biliary abnormalities (with the exception of Gilbert's syndrome or asymptomatic gallstones).
17. **Any history or presence of clinically relevant** cardiac or cardiovascular, gastrointestinal, hepatic, renal, metabolic, haematological, neurological, osteomuscular, articular, psychiatric, systemic, ocular, or infectious disease or immunodeficiency, or signs of acute illness, or any other illness or condition that, in the opinion of the investigator (in consultation with the medical monitor), would adversely affect the participant's participation in this study.
Note: Atopic diseases, like allergic rhinitis or atopic dermatitis, are not exclusionary.
18. **History of cancer:** a previous history of cancer in remission for less than 5 years prior to screening (except for localised carcinoma of the skin that had been resected for cure) or current malignancy.
19. **A positive drug/alcohol test** before dosing, OR any history of drug abuse OR regular alcohol consumption within 6 months of the study defined as:
 - An average weekly intake of > 14 units alcohol. One unit is equivalent to 8 g of alcohol: a half-pint (~240 mL) of beer, 1 glass (125 mL) of wine or 1 (25 mL) measure of spirits.

20. **Current smokers or ex-smokers** who have given up smoking for < 12 months and/or have a smoking pack history of > 5 pack years (1 pack year = 20 cigarettes per day for 1 year or 5 cigarettes per day for 4 years).

21. **Urinary cotinine levels** indicative of smoking or history or regular use of tobacco- or nicotine-containing products within 6 months prior to screening.

22. **Anticipated non-availability and/or risk of non-compliance** with study visits and procedures, or unwillingness or inability to follow the procedures outlined in the protocol.

NOTE: Vulnerable Subjects (e.g those in detention) and those not able to communicate in the native language of the attending study site would be excluded.

23. **The participant has participated in a clinical trial** and has received an investigational product within the following time period prior to the first dosing day in the current study: 3 months, 5 half-lives or twice the duration of the biological effect of the investigational product (whichever is longer).

24. **Exposure to more than 4 investigational medicinal products** within 12 months prior to the first dosing day.

25. **History of sensitivity to any of the study medications**, or its components, or a history of drug reaction or other allergy that, in the opinion of the investigator or Medical Monitor, contraindicates their participation.

NOTE: This includes any previous allergic reaction to biologic agents.

26. **Major surgery** within 90 days prior to screening, or planned in-patient surgery or hospitalisation during the study period

27. **Donation or loss of blood** or blood products in excess of 500 mL within the 3 months before dosing.

28. History of **renal disease**, abnormal kidney function or evidence of persisting or clinically relevant protein or blood on urinalysis.

29. History or signs of **immunologically active disease** (including the presence of low C3 or low C4) or thrombocytopenia.

30. History of **vasculitis**.

CONCOMITANT MEDICATIONS

31. **Prohibited Medications:** Participants are excluded if they are undergoing desensitization therapy, or have received any of the following medications as indicated prior to screening:

- anti- Immunoglobulin E (IgE) therapy (within 6 months)
- anti-IL5 (within 6 months)
- oral or injectable corticosteroids (within 8 weeks)
- long acting muscarinic antagonist (LAMA) or leukotriene receptor antagonist (LTRA) therapy (within 8 weeks)
- drugs that can prolongate the QT interval (see [Table 3](#))

OTHER
32. Employment: participants who are employees of the sponsor or clinical unit are excluded.
33. Vulnerable subjects, e.g., participants kept in detention, protected adults under guardianship, trusteeship and soldiers, or participants committed to an institution by governmental or juridical order.

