
 ▪ Alterations in immune response, potentially leading to increase in infections 	
 ▪ This is a theoretical concern with drugs that affect the immune system. The known biology of IL-5 and eosinophils suggest that inhibiting IL-5 is unlikely to induce an immunosuppressive effect. ▪ Eosinophils may be involved in the immunological response to some helminth infections. 	
 ▪ Individuals with a recent history of an opportunistic infection, a current respiratory or other latent/chronic infection, or positive history or test for hepatitis B/C or human immunodeficiency virus (HIV) are excluded. ▪ Receipt of a live vaccine within 4 weeks of screening is exclusionary, and live vaccines are contraindicated during the study period. ▪ Major surgery within 90 days of screening and/or planned surgery during the study are exclusionary. ▪ Current study will be conducted in countries where gastro-intestinal parasitic infections are rare. Patients with parasitic (helminth) infections within 6 months of screening are excluded, along with those who have travelled to (within the 6 months before dosing) or intend to travel to (within 1 year after dosing) countries with a high prevalence of parasitic disease.

 ▪ Risk of GSK3511294 affecting an unborn baby. 	
 ▪ Reproductive studies have not been conducted with GSK3511294; however, in the 6-month repeat dose monkey study no changes were observed in reproductive organs. Seminiferous tubules were evaluated with respect to their stage in the 	
 ▪ Females of reproduction potential will be excluded from the study.

Potential Risk of Clinical Significance	Summary of Data/Rationale for Risk	Mitigation Strategy

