
 ▪ Duration of the study 	
 ▪ Final follow-up at all dose levels is scheduled to exceed 5 terminal $t_{1/2}$ of GSK3511294 (predicted $t_{1/2}$ is about 37 days; shortest time to follow-up after dosing is 225 days). Owing to the increased affinity of GSK3511294 for IL-5, blood eosinophils levels may still be reduced at the final scheduled follow-up visit, particularly at higher dose levels. However, reduction in blood eosinophils is not considered to be a safety concern – residual levels of blood eosinophils are expected to be present, and there have been no safety signal from chronic dosing with mepolizumab, reslizumab or benralizumab. 	
 ▪ Follow-up will be extended in any participant for whom there are safety concerns, until that concern is discharged.

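### Exclusion criterion 10 and section 6.9.4 end the travel look-back at screening, while the risk table runs it to dosing, leaving up to 28 days before dosing uncovered (minor)

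*Protocol*

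**What the plan says.** Three places in the current protocol text state the travel restriction.

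- **Section 5.2, criterion 10** excludes people who have visited places "with a high prevalence of such infections in the 6 months before screening, or intend to do so in the year after dosing".
- **Section 6.9.4 (Travel)** repeats these two windows as a restriction on participants: six months back from screening, one year forward from dosing.
- **Section 4.7.1 (risk table, row on altered immune response and infection)** describes the mitigation this way: "Patients with parasitic (helminth) infections within 6 months of screening are excluded, along with those who have travelled to (within the 6 months before dosing"; its forward limb is one year after dosing.

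The other look-backs with a stated length in that same mitigation cell are tied to screening: "Receipt of a live vaccine within 4 weeks of screening is exclusionary" and "Major surgery within 90 days of screening and/or planned surgery during the study are exclusionary". The helminth infection window is tied to screening too. Only travel is tied to dosing.

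Section 4.2 allows up to 28 days for screening and admits participants the day before dosing. Note 2 to the Time and Events Table (section 7.1) gives screening as up to 4 weeks before randomisation. Section 5 does not permit deviations from the eligibility criteria.

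**The concern.** The risk table describes a travel exclusion that runs without a break from six months before dosing to one year after it. The rule that sites apply has a hole in it: the look-back stops at screening and the forward limb starts only at dosing. The days left out are those closest to a single dose with a predicted half-life of about 37 days (section 4.6).

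The reason for the exclusion is given in the risk table: "Eosinophils may be involved in the immunological response to some helminth infections". A person could return from a high-prevalence country shortly before admission and still satisfy criterion 10 as worded, although the risk table says such a person is excluded. What is at stake is whether a stated safety mitigation is fully delivered. No statistical quantity depends on it.

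**Working it through.** The protocol gives no figure to reproduce. The check compares the windows and then does date arithmetic.

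**Inputs**

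- S = days from screening to dosing, at most 28 (section 4.2). Section 7.1, note 2, counts 4 weeks (4 × 7 = 28 days) to randomisation, which is assumed to be close to dosing.
- M = six months = 183 days (assumption; 182 to 184 also tried).
- Admission is on Day -1 (section 4.2).

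**Windows, in days before dosing**

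| Source | Look-back covers | Forward limb starts |
|---|---|---|
| Section 4.7.1 | M to 0 | dosing |
| Criterion 10 and section 6.9.4 | S + M to S | dosing |

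The part of the risk-table window that criterion 10 misses is S to 0, which is S days. As a share of the stated window it is S / M:

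- S = 28: 28/183 = 15.3% (28/182 = 15.4%; 28/184 = 15.2%)
- S = 14: 14/183 = 7.7%
- S = 7: 7/183 = 3.8%

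Because of admission on Day -1, about 28 − 1 = 27 of the 28 days allow travel: 27/183 = 14.8%.

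**Two examples with S = 28**

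- *Trip 10 days before dosing.* Risk table: 10 is within 183, so excluded. Criterion 10: the trip falls after screening (10 < 28) and before dosing, so neither limb applies.
- *Trip 200 days before dosing.* Risk table: 200 exceeds 183, so allowed. Criterion 10: 200 lies between 28 and 28 + 183 = 211, so excluded.

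Criterion 10 thus shifts a window of equal length earlier: it loses S days next to dosing and gains S days at the far end.

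**Does another rule close the gap?**

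- Live vaccine (criterion 11) and surgery (criterion 26) also look back from screening, but their forward limbs refer to the study or study period and do not wait for dosing. Travel has no such bridge.
- Criterion 17 concerns disease or illness and rests on the investigator's opinion.
- Criterion 8 excludes people at risk of infection but does not name travel, so someone must first judge that a given trip creates that risk.
- Re-checking eligibility before dosing applies the same wording. A trip after screening is still not a trip before screening.

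**After the change.** With the look-back ending at dosing, the uncovered part of the risk-table window is 0 days.

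**The case against.** The strongest reply is that the risk table may be the side in error. Criterion 10 and section 6.9.4 agree with each other, look-backs ending at screening are usual in this protocol (criteria 1, 8, 9 and the infestation part of criterion 10), and the neighbouring windows in the risk-table cell use screening. Changing one word in section 4.7.1 would remove the contradiction and leave eligibility alone. Sites work from sections 5.2 and 6.9.4, so they receive no conflicting instruction.

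Much of this is fair. Ending a look-back at screening is not a fault in itself, and the protocol does not say which anchor was intended. But aligning the risk table downward would keep an unprotected interval just before a single long-acting dose. There is also precedent for the other direction: Amendment 3 moved the eosinophil pre-screen window from screening to dosing as the correction of an error (section 12.10.3, Changes 2 and 3).

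Criterion 8 deserves some credit. Once a traveller is judged to be at risk of infection, exclusion is mandatory. That narrows the gap in practice, but a case-by-case judgement is not the definite exclusion that the risk table states.

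The objection on importance stands. The protocol says of the infection risk that "This is a theoretical concern with drugs that affect the immune system", adds that "Current study will be conducted in countries where gastro-intestinal parasitic infections are rare", and holds that "reduction in blood eosinophils is not considered to be a safety concern". The percentages above measure overlap of wording, not risk.

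**Conclusion.** The inconsistency is real and minor. The travel rule in criterion 10 and section 6.9.4 leaves out the interval from screening to dosing, at most 28 days (about 27 in which travel is possible), which the risk table says is covered. That is up to 15.3% of the stated look-back, taking six months as 183 days and randomisation as close to dosing. The protocol gives no frequency of travel or infection, so no number of affected participants can be stated. No endpoint, sample size, estimate or error rate changes. It is worth correcting because the correction is cheap and affects who may be dosed.

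**What to change.** In criterion 10 and section 6.9.4, tie the travel look-back to the six months before dosing. That matches section 4.7.1 and closes the gap, but gives up the early days that criterion 10 now covers (up to 28). To keep those as well, word it as running from six months before screening until dosing, and align the risk table to that.

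Confirm travel history at admission or before the dose, as part of any eligibility check already scheduled then.

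The cost is a wording change in two places (three with the longer window) and one question. The downside is that an occasional participant is deferred or excluded after passing screening.

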6.10.2. Prohibited Medications and Non-Drug Therapies

Participants must abstain from taking prescription or non-prescription drugs (including vitamins and dietary or herbal supplements), within 7 days or 5 half-lives (whichever is longer) prior to study medication administration and until completion of the follow-up visit, unless in the opinion of the Investigator and sponsor the medication will not interfere with the study. This excludes the background asthma standard of care defined in Section [6.10.1](#), which are permitted based on the established inclusion/exclusion criteria.

The following asthma medications are prohibited during the study and within the timeframe indicated in brackets before screening:

- Immunotherapy (at any time)
- Desensitization therapy (ongoing)
- anti-IgE therapy (within 6 months)
- anti-IL5 (within 6 months)
- oral or injectable corticosteroids (within 8 weeks)
- LAMA or LTRA therapy (within 8 weeks)
- Live vaccines

Medications that are known to prolong QT interval are also excluded. Some of the more commonly encountered drugs that are known to prolong QT interval are listed in [Table 3](#).

Table 3 Drugs that can prolong the QT interval

Antimicrobials	Antipsychotics (all have some risk)	Antiarrhythmic s	Antidepressants	Antiemetics	Others
Erythromycin	Risperidone	Dronedarone	Citalopram/ escitalopram	Ondansetron/	Methadone
Clarithromycin	Fluphenazine	Sotalol	Amitriptyline	Granisetron	Protein
Moxifloxacin	Haloperidol	Quinidine	Clomipramine	Droperidol	kinase
Fluconazole	Pimozide	Amiodarone	Dosulepin	Domperidone	inhibitors e.g.
Ketoconazole	Chlorpromazine	Flecainide	Doxepin		sunitinib
	Quetiapine		Imipramine		Some
	Clozapine		Lofepramine		antimalarials
					Some
					antiretrovirals
					Telaprevir
					Boceprevir

Notes: list taken from http://www.ggcprescribing.org.uk/media/uploads/ps_extra/pse_21.pdf.

Attenuated or non-live vaccines are prohibited within 5 days before and after dosing.

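### The note to exclusion criterion 11 accepts attenuated vaccines, which are ordinarily live, and so contradicts the live-vaccine exclusion it belongs to

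*Protocol*

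**What the plan says.** Criterion 11 in section 5.2 of the Protocol excludes a participant for a live vaccine "within 4 weeks prior to screening, or intention to receive live vaccine during the study". The note beneath it reads "Attenuated or non-live vaccines are acceptable, if > 5 days before dosing".

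The risk table in section 4.7.1 gives the same exclusion as a mitigation for altered immune response, with no exception for attenuated products: "Receipt of a live vaccine within 4 weeks of screening is exclusionary, and live vaccines are contraindicated during the study period".

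Section 6.10.2 lists live vaccines among the treatments prohibited during the study and closes with "Attenuated or non-live vaccines are prohibited within 5 days before and after dosing". It also requires abstention from other medication "within 7 days or 5 half-lives (whichever is longer) prior to study medication administration", which can be set aside: "unless in the opinion of the Investigator and sponsor the medication will not interfere with the study".

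Section 5 states the standing of the criteria: "Deviations from inclusion and exclusion criteria are not allowed".

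**The concern.** The note treats *attenuated* and *non-live* as two different things and accepts both. The plain meaning of an attenuated vaccine is a live organism that has been weakened, and nothing in the protocol redefines the word to mean inactivated. The note therefore admits a class of live vaccine on a 5-day limit, while the criterion bars live vaccines for the whole 4 weeks before screening.

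A site screening a participant with a recent live-attenuated vaccine can reach opposite eligibility decisions from two adjacent sentences. Because section 5 forbids deviations, the text should not support both. What is at stake is a named safety mitigation in a first-in-human study; no statistical quantity is involved.

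**Working it through.** The protocol gives no figure to reproduce. The check sets the rules on one time scale, days before dosing.

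**Inputs**
- Criterion 11: look-back of 4 weeks (28 days) before screening.
- Note to criterion 11: acceptable if more than 5 days before dosing.
- Section 6.10.2: general abstention of 7 days before dosing. The alternative of 5 half-lives is not applied to a vaccine.
- Sections 4.2 and 7.1 (note 2): screening up to 28 days before randomisation. Randomisation is taken as the dosing day.

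**Definitions**
- S = days from screening to dosing.
- d = days from vaccine to dosing.

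**Rules**
- The criterion excludes d from S + 1 to S + 28.
- The note accepts d > 5.
- The abstention covers d ≤ 7.
- Clear conflict: d is in the criterion's range, is accepted by the note, and is beyond the abstention, so d ≥ 8.

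| S | Criterion excludes d | Note accepts, of these | Also beyond the 7-day abstention |
|---|---|---|---|
| 28 (protocol maximum) | 29 to 56 | 28 days | 28 days |
| 14 (assumed) | 15 to 42 | 28 days | 28 days |
| 7 (assumed) | 8 to 35 | 28 days | 28 days |
| 2 (assumed minimum) | 3 to 30 | 25 days (6 to 30) | 23 days (8 to 30) |

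For any S ≥ 7 the nearest excluded day is S + 1 ≥ 8, so the whole 28-day look-back lies beyond both the 5-day and the 7-day limits.

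**Single case.** For a live-attenuated vaccine 14 days before screening, d = 14 + S, which is at least 15 for any S ≥ 1. The criterion excludes the participant, since 14 is less than 28. The note accepts the vaccine, since 15 is more than 5. The abstention does not apply, since 15 is more than 7.

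**The screening period.** The criterion also bars intended live vaccination during the study. If that phrase includes screening, as section 4.2 suggests by counting screening in the study duration, then at S = 28 a further 21 days (8 to 28) conflict. Days 6 to 7 would conflict on the same condition, but they also fall under the waivable abstention. These days are conditional and are not counted as clear conflict.

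**After dosing.** No conflict is claimed. The closing sentence of 6.10.2 only prohibits; it permits nothing outside its 5-day window, and the list above it still bans live vaccines.

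**The case against.** The strongest reply is that the contradiction depends on a definition the protocol does not give. The protocol puts *live* in the criterion and *attenuated* in the note, so its own usage could be read as two categories with two windows. Notes in section 5.2 do sometimes work as exceptions: the note to criterion 6 readmits some hepatitis C antibody-positive participants, and the note to criterion 17 exempts atopic disease.

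That reading does not hold up. Most live vaccines are attenuated, so such an exception would leave the criterion little to exclude, and it would conflict with the unqualified statement in 4.7.1. That other notes do modify their criteria adds to the difficulty, because a site could reasonably follow this one too.

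A second reply is that the word is a slip for *inactivated* and that the intended rule can be recovered. This is probably right. The criterion and 4.7.1 point that way, and so does the rationale recorded for Amendment 4 (Appendix 10), which says live vaccines are not allowed at any time during participation. But this explains the error and does not remove it: sites apply the text as written, and no rule says the criterion prevails over its note.

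What stands is the point about consequence. Section 4.7.1 says of the infection risk: "This is a theoretical concern with drugs that affect the immune system". At the maximum screening interval every day of clear conflict is more than four weeks before dosing; shorter gaps need shorter screening intervals, which are assumed here. The day counts measure how far the rules overlap, not harm.

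**Conclusion.** The note contradicts its criterion and the risk table. The clear conflict covers the full 28 days before screening whenever screening is at least 7 days before dosing: days 29 to 56 before dosing at the 28-day maximum, and days 15 to 42 at an assumed 14 days.

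The conclusion rests on the ordinary meaning of *attenuated*, which the note's own contrast with *non-live* supports, and on taking randomisation as the day of dosing for the day counts. The protocol gives no basis for estimating how many participants would have had such a vaccine.

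The practical weight is small. The point should still be corrected, because it sits in an operative eligibility rule that allows no deviation and gives two answers to the same question.

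**What to change.** Replace *attenuated or non-live* with *inactivated or other non-live* in the note to criterion 11 (section 5.2) and in the last line of section 6.10.2. The second change keeps the wording consistent. State once, most usefully in criterion 11, that live-attenuated vaccines count as live vaccines. Section 4.7.1 needs no change.

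The cost is a wording change in two places plus one clarifying statement, with no effect on sample size, analysis or study conduct beyond making the rule unambiguous.
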